## **Additional Exploratory Analyses**

### **1. Age and sex**

While older patients tend to be aware of their increased vulnerability, younger patients may be more surprised to learn of their high-risk status. Additionally, our previous work suggests that males and females are differentially likely to get vaccinated as a function of age, with younger females *more* likely to get vaccinated than males, and older females *less* likely to get vaccinated than older males.

To test the relation between flu shots, age and sex, we will run an OLS regression including binned patient age (18–24, 25–34, 35–44, 45–54, 65+), sex, and their interaction.

Additionally, we will test for an interaction between age, sex, and study arm, as people of different ages and sexes may be differentially receptive to different alert versions.

We may also test whether alert effectiveness varies by clinician age and/or sex.

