In order to generate flu risk scores, Medial EarlySign has access to a de-identified, retrospective dataset in Geisinger's research environment. This environment is accessed by Medial EarlySign staff who have undergone appropriate training and are credentialed per Geisinger's research and Information Security/Access policies. This environment is protected by Geisinger Information Security Office standards that allow remote access to the Geisinger network in a 'sandbox'. All data and analysis are conducted within the secure environment and data do not leave the Geisinger network. The dataset contains EHR information on all patients who had a primary care encounter at Geisinger (outpatient or telemedicine) between 10/1/2008 and 4/13/2022.

Medial uses the retrospective dataset to generate flu risk scores for patients in that dataset who meet the following criteria:

1. Were born in the year 2004 or later (i.e., those turning 18 in the year 2022 and older)
2. Were alive according to the EHR as of April 2022 when the dataset was last updated
3. Either:
 - a. Currently have a Geisinger PCP assigned
 - b. Have been in the EHR since at least September 2021 AND have had at least one encounter in 2020–2022

After we obtain the base sample list from Medial, **Business Intelligence & Advanced Analytics** (BIAA), working with **Geisinger's Phenomics and Clinical Data Core** (PACDC), will pull a dataset to help us determine who meets our inclusion criteria and aid in NIH demographics reporting. This dataset will include demographic information, including patient birth date, race, ethnicity, and gender and/or sex. Finally, the dataset will include death date to ensure patients are living as of the date the data are extracted.

We will also obtain individual-level employee demographic information including age, gender, race, and ethnicity for provider-participants to aid in NIH demographics reporting. This information will be deidentified and aggregated prior to any external reporting or data sharing.

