## Power Analysis

We expect at least 60,000 patients to be enrolled (at least 20,000 per arm). With this sample size, we will have 80% power to detect an increase in flu vaccination rates from 35% to 36.34% with two-tailed alpha = .05 for any comparison between arms.

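### The age bins for the exploratory age-by-sex analysis leave out ages 55–64, probably a typing slip, and the effect depends on coding the SAP does not state

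*SAP*

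**What the plan says.** The section on age and sex sits under "Additional Exploratory Analyses" in the SAP. It defines age through five categories, in a planned "OLS regression including binned patient age (18–24, 25–34, 35–44, 45–54, 65+), sex, and their interaction". The stated motive is that "our previous work suggests that males and females are differentially likely to get vaccinated as a function of age": the SAP expects women to be vaccinated more often than men at younger ages and less often at older ages. The next step is described as follows: "Additionally, we will test for an interaction between age, sex, and study arm". No separate age coding is given for that test.

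The protocol's inclusion criteria (Study Population, Patients) set a minimum age of 18 and no maximum. Its Data Sources section glosses the patients who receive a risk score as "those turning 18 in the year 2022 and older". Neither document excludes ages 55–64, gives another set of bins, names a reference bin, or says how to treat a patient whose age falls outside the listed bins.

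**The concern.** A patient aged 55 to 64 is eligible, can be randomised and enrolled, and has no place in the planned age variable. From 25 up the bins run in ten-year steps, and only the step before 65+ is absent. This suggests a dropped bin or a mistyped limit rather than a decision to leave the group out.

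Two things are at stake. First, the analysis is meant to trace how the sex difference changes, and is expected to reverse, with age. A ten-year hole between the middle and oldest bins lies inside the range over which that change would be traced. Second, statistical software will treat these patients differently according to how the bins are programmed, and the SAP does not settle this. If the report later uses six bins, a reader could not tell whether that was the plan or a departure from it.

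**Working it through.** **The SAP's own calculated figure.** The power statement (80% power, 35% versus 36.34%, 20,000 per arm, two-sided alpha 0.05) uses no age bins. It is reproduced here only to show that it stands apart from this point.

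- Mean rate = (0.35 + 0.3634)/2 = 0.3567.
- SE = √(2 × 0.3567 × 0.6433 / 20,000) = 0.00479.
- z = 0.0134/0.00479 = 2.797, and 2.797 − 1.960 = 0.837, so power = Φ(0.837) = 0.799. This agrees with the stated 80%.

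**Coverage of the bins.** Inputs: the five SAP bins and the protocol's minimum age of 18. Checking each whole-year age from 18 to 100 leaves exactly ten uncovered: 55, 56, …, 64. With a 55–64 bin added, no age is uncovered and none is counted twice.

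**What the regression does with these patients.** With sex as two categories, complete coverage in six bins gives 6 × 2 = 12 age-by-sex cells, or 12 × 3 = 36 with three arms. Parameters = intercept + age terms + sex + age-by-sex terms; multiply by 3 when fully interacted with arm.

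| Coding | Parameters | Age-by-sex cells with data in the model | With three arms | Ages 55–64 |
|---|---|---|---|---|
| (a) Five-level factor, 55–64 missing | 1+4+1+4 = 10 | 10 | 30 for 30 | dropped |
| (b) Four indicators, one listed bin as reference | 1+4+1+4 = 10 | 12 | 30 for 36 | merged with the reference bin |
| (c) Five indicators plus intercept | 1+5+1+5 = 12 | 12 | 36 for 36 | unnamed reference |
| Corrected, six bins | 1+5+1+5 = 12 | 12 | 36 for 36 | own bin |

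- Under (a) the model is saturated in the listed cells, so the point estimates for those bins do not change. There is no result for 55–64. The age-by-sex interaction test has 5 − 1 = 4 degrees of freedom instead of 6 − 1 = 5. The age-by-sex-by-arm test has 4 × 2 = 8 instead of 5 × 2 = 10, if it uses the same bins.
- Under (b), for each sex the reference-cell mean moves by w × (m₅₅₋₆₄ − m_ref), where m is the vaccination rate in that cell and w = n₅₅₋₆₄/(n₅₅₋₆₄ + n_ref). Every contrast against the reference bin moves by that amount with the opposite sign. The shift is zero only if the two rates are equal. The documents give no rates by age, and the SAP itself expects the sex difference to vary with age, so equality cannot be assumed. With 18–24 as reference (an assumption), patients aged 55–64 would be pooled with the youngest adults.
- Under (c) no one is lost, but all contrasts are against a group the SAP never names.

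**Number of patients.** The documents give no age mix, so this cannot be calculated. For illustration only, assume that 5–30% of enrolled patients are aged 55–64:

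- SAP minimum: 60,000 × 0.05 = 3,000 to 60,000 × 0.30 = 18,000, or 1,000 to 6,000 per arm of 20,000.
- Protocol's anticipated enrolment: 90,000 × 0.05 = 4,500 to 90,000 × 0.30 = 27,000.

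The analysed number would be lower to the extent that the SAP's restriction to first in-person appointments removes patients.

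**The case against.** The strongest reply is that this is a proofreading matter. The pattern of the bins makes the slip obvious, an analyst would very likely see and correct it, and nothing confirmatory depends on it. That stands, and it is why the point is minor.

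A second reply is that (b) and (c) are programming accidents rather than readings of the plan. Binned age ordinarily means a categorical variable, so (a) is the plain reading, and under (a) the listed bins are estimated correctly. This stands in part. Coding (a) is the likeliest, but hand-built indicators are common and the SAP does not rule them out. Even (a) leaves an eligible group without a result. It is also fair to say that an unstated reference level is not a defect in itself. With complete bins the choice would not change the fitted values; it matters here only because of the gap.

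Third, the parameter counts only restate that a bin is missing, and the patient range rests on an assumed share. Both are true. The counts show which codings lose or merge cells, but they do not measure bias, and the patient range should be read as illustration. It can be added that under (b) precision changes as well, because the reference group grows even where rates are equal.

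Finally, the three-way test follows directly after the bins, so the natural reading is that they carry over. That is probably right, and it would extend the gap to that test.

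The list is an unbroken parenthesis in running text, with no sign of a broken table or a redaction. An item lost in reading the PDF cannot be wholly excluded, but nothing points to it.

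**Conclusion.** The concern holds. The omission of ages 55–64 is certain from the text; that it is a typing slip is an inference. Followed as written, the plan drops an eligible ten-year group, merges it with another bin, or makes it an unnamed reference, according to coding the SAP leaves open. Measured against six-bin coding, the five-level reading has 10 of 12 age-by-sex cells and 4 of 5 interaction degrees of freedom, and 30 of 36 cells and 8 of 10 degrees of freedom in the three-way test if the bins carry over.

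The effect on estimates cannot be sized, because the documents give neither the age mix nor vaccination rates by age. Severity is minor: only the exploratory age-by-sex and, probably, age-by-sex-by-arm analyses are touched. Analyses 1 and 2 and the 80% power statement are unaffected.

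**What to change.** In the SAP's section on age and sex, correct the list so that the bins cover every age from 18 up without overlap. The most natural correction is 18–24, 25–34, 35–44, 45–54, 55–64, 65+. If a limit was mistyped instead, correct that limit, for example to 45–64 or to 55+. Either of these keeps five bins, and so 10 age-by-sex cells and 4 interaction degrees of freedom, but with every patient included. State in the same place that the age-by-sex and age-by-sex-by-arm models use the same bins.

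The cost is a one-line correction, with no effect on sample size, power or the confirmatory analysis. It is best made and dated before the age analyses are run, so that the bins in the report can be recognised as the planned ones.

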### **2. Risk level**

We will explore heterogeneity in flu vaccination rates within the top 20% of risk and test whether effects of study arm vary as a function of risk level.

### **3. Number of appointments**

Patients may have more than one appointment scheduled during the study where the flu BPA fired. We will explore whether vaccination rates were higher with more appointments for those in the experimental groups compared to those in the control group with the same number of appointments.

### **4. Appointment department/specialty**

Some departments give more flu shots than others. We will test if the alert versions are differentially effective as a function of department or specialty, to see if some versions are particularly helpful for under-performing departments or specialties.

### **5. Contamination analysis**

Although randomization was at the patient level, the intervention was directly experienced by clinicians rather than patients. Many clinicians encountered patients and their assigned BPAs for all three experimental arms. We will explore whether contamination was present in our data due to clinicians' exposure to multiple experimental conditions (e.g., by examining results as a function of clinic-level variation

in the number of patients randomly assigned to each arm and/or as a function of the duration of exposure to the information).
